## Abstract

Certain mood stabilizer/anticonvulsant medications may be better suited for epilepsy with comorbid psychiatric illness. Many anticonvulsants are broad-spectrum and are well established as improving outcome for epilepsy as well as for behavioral disorders. The intuitive choice for treatment in patients with such comorbidity would be medications with an established track record in successfully treating both conditions independently. Benzodiazepines are a mainstay of anxiety treatment as well as for epilepsy treatment.

Given its unique molecular structure, clobazam (Onfi®) is an example of a medication that theoretically could serve a “dual role” in terms of treating epilepsy as well as anxiety disorder. Anxiety is prominent in children and adolescents with epilepsy although the evidence base is underdeveloped.

This study would assess the utility of clobazam, which may represent a more effective and better tolerated treatment option for the numerous patients with seizure disorders who also have anxiety. This study is an investigator initiated proposal submitted by the PI and is a prospective open-label clinical trial of 20 children and adolescents with epilepsy. The assessments include standardized questionnaires widely used in clinical practice as well as structured psychiatric diagnostic tools. Overall, this study will contribute valuably to an understudied patient population and add key information to the evidence base that potentially will make an immediate clinical impact.

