## Overview of Study Design

This study is an open label, adjunctive, proof of concept, pilot clinical trial. Prospective participants will be identified from chronic epilepsy clinical populations of Johns Hopkins Hospital and Kennedy Krieger Institute. Pediatric participants will be considered for the study if neurologic status suggests the need for additional treatment, and behavioral characteristics are clinically significant. All participants will receive active treatment, involving flexible dose titration of clobazam and will be monitored for a period of four months. The study will be monitored and overseen by the Johns Hopkins Hospital Institutional Review Board.

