potential adverse events. Flexibility with minimum or maximum dosages will be employed in order to meet clinical needs.

Participants will be considered to have completed the study if they have successfully completed in-person visits. Participants will be free to withdraw from the study at any time by their choice, or if adverse events are intolerable or other risks outweigh potential benefits then participants will be terminated from the study. Participants who withdraw early for any reason will be assessed for safety, discharged from the study and returned to the care of their primary neurologist.

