#### **Statistical Analysis Plan**

Change from baseline will be analyzed statistically to test the main study hypotheses--that Onfi® has a dual role of improving both behavioral/psychiatric status, namely anxiety symptoms, as well as seizure control, in patients with epilepsy.

Outcome measures will encompass behavioral and neurologic status. The primary outcome variable will be Clinical Global Assessment of Functioning Improvement from baseline. CGI ratings will be attributed both to neurological status including seizure control, as well as behavioral status. CGI-Improvement ratings of a 1 or 2 (on a 7 point scale) will be considered positive responses. Paired student's t-tests will be used to compare baseline and study endpoint ratings for response versus non-response.

Secondary outcome measures will include changes from baseline in overall and subscale ratings of the Pediatric Anxiety Rating Scale (PARS), Multidimensional Anxiety Scale (MASC), and the Quality of Life in Epilepsy Scale. Positive outcomes will be defined as 10% score reduction or scores that drop below threshold of clinical significance. Paired student's t-tests will be used to compare baseline and study end outcomes for each measure.

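### The primary test does not fit the primary outcome: CGI-Improvement has no baseline value, so a paired t-test of baseline against endpoint cannot test response

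*Combined protocol and SAP*

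**What the plan says.** The Abstract describes a "prospective open-label clinical trial of 20 children and adolescents with epilepsy". The Overview of Study Design adds that "All participants will receive active treatment, involving flexible dose titration of clobazam", so there is one arm and no control.

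The Statistical Analysis Plan section sets out the primary analysis in four steps:

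- Outcome: "The primary outcome variable will be Clinical Global Assessment of Functioning Improvement from baseline".
- Domains: "CGI ratings will be attributed both to neurological status including seizure control, as well as behavioral status".
- Response rule: "CGI-Improvement ratings of a 1 or 2 (on a 7 point scale) will be considered positive responses".
- Test: "Paired student's t-tests will be used to compare baseline and study endpoint ratings for response versus non-response".

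The section presents the analysis of change as a test of the main hypotheses, namely that the drug improves both anxiety and seizure control. It gives no alpha, sidedness, success criterion or reference response rate. It plans no responder proportion, confidence interval or binomial test. No severity rating or other baseline global score is named anywhere in the document.

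**The concern.** A paired t-test needs the same quantity measured twice in each participant. An improvement rating is itself the comparison with baseline, so each participant has one value, at follow-up. The response flag derived from it cannot vary at baseline either. The plan therefore asks for a comparison whose first half is undefined.

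This is the only analysis given for the primary outcome, and it is meant to carry the dual-role hypothesis. An analyst would have to choose a reading, possibly after seeing the data. Some readings can give p<0.05 with few or no responders; the others do not test response at all.

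The responder count is also undefined until it is settled whether neurological and behavioral status share one CGI-I or have one each.

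The uncontrolled pilot design is openly stated and is not the defect. The defect is the mismatch between test and outcome.

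**Working it through.** The plan states no figure for this analysis, so there is none to reproduce. The check takes each possible reading of the test in turn.

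**Inputs.** From the documents: n=20 (Abstract); response is CGI-I of 1 or 2 on a 7-point scale (Statistical Analysis Plan). Assumed, because the documents are silent: two-sided alpha 0.05; 15 evaluable as an example of attrition; response rates without drug effect of 10% to 40%.

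**Reading 1: response coded 0/1, with baseline 0 for everyone.** With k responders the differences are k ones and n−k zeros. The mean is k/n and the standard error is √[k(n−k)/(n²(n−1))], so

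t = √[k(n−1)/(n−k)], with n−1 degrees of freedom.

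- n=20, k=3: √(3×19/17) = 1.831; two-sided p=0.083, one-sided p=0.041.
- n=20, k=4: √(4×19/16) = 2.179; two-sided p=0.042.
- n=15, k=3: √(3×14/12) = 1.871; two-sided p=0.082.
- n=15, k=4: √(4×14/11) = 2.256; two-sided p=0.041.

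Four responders are enough in either case (three of 20 at one-sided 0.05). The exact (Clopper-Pearson) 95% intervals at that point are 5.7% to 43.7% for 4/20 and 7.8% to 55.1% for 4/15. The test only asks whether the response rate is 0%.

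The chance of reaching that threshold when the drug adds nothing is P(X≥4) = 1 − Σ C(n,x) pˣ(1−p)ⁿ⁻ˣ, summed over x=0 to 3:

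| Assumed response rate without drug effect | n=20 | n=15 |
|---|---|---|
| 10% | 13% | 6% |
| 20% | 59% | 35% |
| 30% | 89% | 70% |
| 40% | 98% | 91% |

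**Reading 2: responders against non-responders.** These are different participants, so there are no pairs and a paired test cannot be computed.

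**Reading 3: raw CGI-I against an assumed no-change value of 4 at baseline.** This is a one-sample t-test against 4 and ignores the 1-or-2 rule. If m participants are rated 3 and the rest 4, then t = −√[m(n−1)/(n−m)].

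- m=4, n=20: t = −√(4×19/16) = −2.179; p=0.042, with 0/20 responders.
- m=10, n=20: t = −√(10×19/10) = −4.359; p=0.0003, with 0/20 responders.

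**Reading 4: a global severity score at both visits.** A paired t-test could be computed, but the plan names no such score, and a change in mean severity is not a test of response.

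**The case against.** The strongest reply is that the sentence speaks of ratings at baseline and endpoint, and that the plan uses the general term CGI as well as CGI-Improvement. A global rating may have been intended at both visits, with CGI-I used only to classify responders. The paired test would then be computable and the fault would be incomplete specification. That is Reading 4. It is plausible, but the score is undefined and the responder rule still has no analysis.

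A second reply is that the primary variable is improvement itself, so a mean CGI-I tested against no change has a meaningful null. That is true for mean improvement, but the plan frames its test as response versus non-response.

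A third reply is that the 13% to 98% probabilities reflect the lack of a control, and that an exact interval does not cure this: even 1/20 has a lower limit of about 0.13%, above zero. This stands. The probabilities show how little a p-value against 0% means; they do not measure a harm that the interval removes. The Reading 3 patterns likewise show what is possible, not what is likely.

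Finally, this is an open-label pilot with no decision rule, and the proportion could be calculated from the collected ratings anyway. That limits the harm. But the plan says it will test hypotheses, and this is the only primary analysis it states.

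**Conclusion.** The concern holds and must be fixed before analysis. As written, the primary test has no defined baseline value, and none of the four readings tests the CGI-I responder outcome against a meaningful null. At an assumed two-sided 0.05, nominal significance needs only 4 responders of 20 under the literal binary reading, and can occur with none when CGI-I is compared with 4.

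The mismatch follows from the plan's own wording and needs no assumption. The sizes rest on the assumed alpha, the assumed numbers evaluable and the assumed response rates without drug effect. Confidence is high. The defect is confined to the primary analysis: paired tests are workable for the secondary scale scores.

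**What to change.** In the Statistical Analysis Plan section:

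- Replace the primary paired t-test with the proportion of participants rated CGI-I 1 or 2 at endpoint and its exact (Clopper-Pearson) 95% confidence interval.
- Define the endpoint rating and the denominator, including how early withdrawals are counted. Study Visits states that "Participants will be free to withdraw from the study at any time by their choice" and also allows care to pass to the primary clinician before the seventh visit.
- Do not cite a p-value against 0%, or an interval that merely excludes 0%, as support for the dual-role hypothesis.
- Use one instrument name, CGI-I, throughout. State whether neurological and behavioral status are one rating or two and, if two, which is primary or how they combine.
- Keep paired tests for the scales scored at both visits: PARS, MASC and the Quality of Life in Epilepsy Scale.
- Only if a test is wanted, use an exact binomial test against a justified non-zero reference rate fixed before analysis. The documents give no such rate. For illustration, against an assumed 30% at one-sided 0.025, 11/20 would be needed (exact size 0.0171; power 0.755 at a true rate of 60%).

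**Cost.** The proportion and interval need only new wording, with no extra patients or data. A baseline severity rating, if one was intended, would have to be specified separately. Two domain ratings could mean extra data collection if only one was planned. The headline becomes less favourable: an estimate with a wide interval, such as 27.2% to 72.8% for 10/20, instead of a p-value.

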**Inclusion criteria:**

- Established diagnosis of epilepsy, characterized by focal seizures with suspected or documented localization in the temporal lobe. All participants will have active epilepsy that requires treatment with anticonvulsant medication.
  - Although it is not necessary to be seizure free, a seizure baseline period will be established in the 60 days prior to enrollment into the study.
  - Current regimen of anticonvulsant drugs must have been stable for 30 days prior to entry into the study.
- No episodes of seizure clusters of status epilepticus within 30 days prior to entry into the study.
- Established symptoms of anxiety with functional impairment.
- Baseline behavioral criteria for inclusion will include subscale scores above the norm for age and gender on one of the following:
  - Pediatric Anxiety Rating Scale (PARS).
  - Multidimensional Anxiety Scale (MASC)
- Male or female participants equal to or above age 6 and below age 18 at the start of the study. No exclusion will be made on the basis of gender or minority status.
- Good general health as determined by medical history and physical examination.
- Ability to swallow pills (participant will receive pill swallowing instruction if necessary). The medicine may be cut into pieces and/or mixed with applesauce.
- If female of childbearing age, a negative urine or serum pregnancy test must be established or assured at baseline. Additionally, the participant must agree to use abstinence or appropriate contraception methods or be otherwise incapable of pregnancy for the duration of the study. Pregnancy test results will be shared with parent or guardian. Pregnancy status (or prevention) and abstinence or contraception methods will be addressed

throughout the study for females of childbearing age as well as for post-pubertal males.

- Previous subjects who failed at any point to meet continuation criteria and withdrew early may be considered for re-enrollment by the PI on a case-by-case basis.
- Participant or legal caregiver capable of providing informed consent and fully capable of monitoring the subject's disease process and compliance with treatment.

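### One decrease-only definition of a positive outcome also covers the quality-of-life scale, whose scoring direction is not stated; if higher means better there, the definition is inverted

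*Combined protocol and SAP*

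**What the plan says.** All the text at issue is in the combined protocol and SAP.

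- **Secondary measures (Statistical Analysis Plan).** "Secondary outcome measures will include changes from baseline in overall and subscale ratings" of three instruments: PARS, followed by "Multidimensional Anxiety Scale (MASC), and the Quality of Life in Epilepsy Scale".
- **Definition of success (next sentence).** "Positive outcomes will be defined as 10% score reduction or scores that drop below threshold of clinical significance". No instrument is exempted, and no reverse scoring is described here or elsewhere.
- **Test (sentence after that).** "Paired student's t-tests will be used to compare baseline and study end outcomes for each measure".
- **Direction of the anxiety scales (Inclusion criteria).** Entry on PARS or MASC needs "subscale scores above the norm for age and gender on one of the following", so a high score is the abnormal one.
- **Size (Abstract).** The study is a "prospective open-label clinical trial of 20 children and adolescents with epilepsy".

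The documents do not say which version of the quality-of-life scale is used, which end of it is favourable, or what threshold would apply to it.

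**The concern.** A rule for success has to point towards improvement on every scale it governs. This one points downwards on three scales, and the documents support a downward direction for only two of them. A scale named for quality of life would ordinarily give higher scores to better quality. If this one does, the rule labels falling scores as positive and cannot label any rise as positive.

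Responder counts are easy to quote from a small single-arm pilot. An inverted count could hide a benefit or present a decline as success. A change of direction made after the data are seen would look post hoc.

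**Working it through.** **Figure to reproduce.** None. The plan gives no expected response rate, power or threshold for this rule.

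**Step 1: logic of the rule.** Let *b* be the baseline score and *e* the end score.

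- First part: (*e* - *b*)/*b* ≤ -10%, which requires *e* < *b*.
- Second part: the score drops below a threshold, which also requires *e* < *b*.

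For positive scores, a child meets the rule only if the score fell. This follows from the wording and needs no distributional assumption.

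**Step 2: example on a scale where higher is better (assumed).**

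- 50 to 44: (44 - 50)/50 = -12%. Positive as written, though quality of life is lower.
- 50 to 60: (60 - 50)/50 = +20%. Not positive as written, though quality of life is higher.

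**Step 3: the other direction.** If higher is worse, a fall is an improvement, the rule works, and 0 of 20 are misclassified.

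**Step 4: illustrative counts.** Only the sample size of 20 comes from the documents. Assumed: higher is better, all 20 children have both scores, and percent change is normal with mean *m* = +10% and SD *s* from 10% to 25%.

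- Rise of at least 10%: 1 - Φ((0.10 - *m*)/*s*) = 1 - Φ(0) = 0.500 at every *s*, or 10.0 of 20.
- Fall of at least 10% (first part of the rule): Φ((-0.10 - *m*)/*s*) = Φ(-0.20/*s*).
- Any fall (upper bound for both parts, since no threshold value is given): Φ(-*m*/*s*) = Φ(-0.10/*s*).

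| SD *s* | Fall ≥ 10% | Of 20 | Any fall | Of 20 |
|---|---|---|---|---|
| 10% | 0.023 | 0.5 | 0.159 | 3.2 |
| 15% | 0.091 | 1.8 | 0.252 | 5.0 |
| 20% | 0.159 | 3.2 | 0.309 | 6.2 |
| 25% | 0.212 | 4.2 | 0.345 | 6.9 |

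The 10.0 of 20 arises only because the assumed mean equals the 10% cut-off. For the same reason, an assumed mean loss of 10% puts exactly 10.0 of 20 in the first part of the rule.

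**Step 5: a second set of assumptions.** A simulation of 1,000,000 draws used a 0 to 100 scale with higher better, baseline mean 60, SD 15 and baseline-to-end correlation 0.5 to 0.85, all assumed. It compared the 10% part as written (*e* ≤ 0.9*b*) with its mirror image (*e* ≥ 1.1*b*).

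| True mean change | As written, of 20 | Mirrored, of 20 |
|---|---|---|
| +10 points | 0.4 to 2.6 | 12.0 to 13.5 |
| -5 points | 9.0 to 9.4 | 2.1 to 4.9 |

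Both models show the same reversal with different counts. They illustrate the logic; they do not size the problem.

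**The case against.** **The direction is assumed.** This stands. The documents do not show that higher is better on this scale. A reader might infer that the plan is definitely inverted, but the documents support only the conditional statement.

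**The rule may have been written for the anxiety scales.** A threshold of clinical significance suits a symptom scale, and the Inclusion criteria give a norm-based criterion only for PARS and MASC. Loose drafting is plausible. The text nevertheless lists all three instruments immediately before the rule and exempts none. If the narrower meaning was intended, the quality-of-life scale has no definition of a positive outcome.

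**The analysis itself is on scores.** This largely stands. A reader might infer that the secondary t-tests carry the same error, because they follow directly after the definition and because the primary analysis is worded as "Paired student's t-tests will be used to compare baseline and study endpoint ratings for response versus non-response". The documents do not support that well. The secondary outcomes are stated as changes from baseline in ratings. A status defined by change from baseline also has no baseline value to pair. The section does not state whether the tests are one- or two-sided; a two-sided paired t-test on raw scores keeps the sign of the mean change and is unaffected.

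**A lower score is not proof of a worse child.** This also stands. A fall can be measurement error, so the accurate statement is that only children whose score fell can be counted, not that each of them deteriorated.

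**Conclusion.** The point holds conditionally and is minor. One decrease-only definition is applied to three measures, and for the third the plan does not show that a decrease is favourable. If higher means better, the classification is inverted for that scale. If higher means worse, nothing is wrong beyond the unstated direction.

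The reach is narrow: one responder classification on one secondary measure. No decision, stopping rule or success criterion in the documents depends on it.

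A reader might take the 10 of 20, or any other count above, as the expected number misclassified. The documents do not support any such number, because they give no expected change, SD or threshold for this scale.

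**What to change.** Before analysis, limit the existing reduction-or-threshold sentence to PARS and MASC, and add for the third measure:

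> For the Quality of Life in Epilepsy Scale ([version], scored so that [higher/lower] values mean better quality of life), a positive outcome is a change of at least 10% from baseline in the overall score in the direction of better quality of life. Any threshold used must be crossed in that same direction.

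The cost is SAP wording only, with no added visits, data or participants. The one demand is that the scale's version and scoring direction be settled before analysis. Naming the overall score also fixes which score decides the classification; subscales can still be reported as changes from baseline.

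### The 10% fall that counts as a positive PARS or MASC outcome has no stated basis and, under assumed retest error, could be met by about 13% to 37% of unchanged children

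*Combined protocol and SAP*

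**What the plan says.** The rule is in the Statistical Analysis Plan: "Positive outcomes will be defined as 10% score reduction or scores that drop below threshold of clinical significance". It follows directly on "Secondary outcome measures will include changes from baseline in overall and subscale ratings" of PARS, MASC and the Quality of Life in Epilepsy Scale, so it covers subscales as well as totals. The plan gives no reason for 10%, no value for the clinical threshold, and no statement of whether raw or normed scores are used. The analysis of these measures is given as "Paired student's t-tests will be used to compare baseline and study end outcomes for each measure".

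The primary outcome has its own rule: "CGI-Improvement ratings of a 1 or 2 (on a 7 point scale) will be considered positive responses".

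Two design features bear on the point. There is no control arm (Overview of Study Design: "All participants will receive active treatment, involving flexible dose titration of clobazam and will be monitored for a period of four months"), and the Abstract gives the size as 20 children and adolescents. Under Inclusion criteria, children enter on high scores: "Baseline behavioral criteria for inclusion will include subscale scores above the norm for age and gender on one of the following", the scales listed being PARS and MASC.

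**The concern.** Anxiety is half of the main hypothesis, and PARS and MASC are the only anxiety-specific outcomes that the plan names; the CGI rating is attributed to neurological and behavioral status together. A responder definition is informative only if a child who has not changed seldom meets it. A cut of 10% may be small compared with the difference between two ratings of a stable child. If so, a good part of the share reported as positive would appear without any treatment effect, and there is no concurrent group to show how large that part is.

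Two features of the rule make this easier. On short scores the smallest possible change can reach 10%. The second route, dropping below the clinical threshold, requires no particular size of fall, so a child just above the threshold can qualify by one point.

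Ten percent is also not one criterion. On a normed score whose average lies well above zero, the SD is small relative to the mean and a 10% fall is a harder test than on a raw score with wide relative spread. The inclusion criteria refer to age and gender norms; the analysis section does not say which version is scored.

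**Working it through.** The plan offers no derivation of the 10%, so there is no figure to reproduce.

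**Inputs.** From the documents: the 10% cut, its use on overall and subscale ratings, 20 children, no control arm. Not in the documents, so assumed: baseline SD as a fraction of the mean score (c) of 0.20 to 0.40, with 0.15 as a favorable case; retest reliability (r) of 0.7 to 0.9, with 0.95 as a favorable case; normal scores; no true change; no selection.

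**1. Point arithmetic (no assumptions).** The smallest whole-point fall that is at least 10% of a score b is b/10 rounded up. For b from 1 to 10 this is 1 point; for 11 to 20 it is 2; for 30 it is 3; for 60 it is 6.

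**2. Chance that an unchanged child falls by at least 10%.** Take the mean as 1. Baseline B and follow-up F each have SD c and correlation r. The rule is met when F − 0.9B ≤ 0. That difference has mean 0.1 and variance c²(1 + 0.81 − 1.8r), so

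P = Φ(−0.1 / [c√(1.81 − 1.8r)]).

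At c = 0.30, r = 0.8: √0.37 = 0.608; 0.30 × 0.608 = 0.1825; 0.1/0.1825 = 0.548; Φ(−0.548) = 0.29.

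| SD / mean | r = 0.7 | r = 0.8 | r = 0.9 |
|---|---|---|---|
| 0.20 | 25% | 21% | 13% |
| 0.30 | 33% | 29% | 22% |
| 0.40 | 37% | 34% | 28% |

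Simulations of this model put the ends of the range at 12% and 38%; the difference of about one point is immaterial. In the favorable case, c = 0.15 gives 6% at r = 0.9 and 2% at r = 0.95.

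**3. In a trial of 20.** At 29%, 20 × 0.29 = 5.8 unchanged children would be expected to count as positive on a given score, and the binomial chance of at least 4 is 0.87.

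**4. Is 10% always inside retest error?** The SD of change between two ratings is c√(2(1 − r)). At c = 0.30, r = 0.8 it is 0.30 × √0.4 = 19.0% of the mean. At c = 0.20, r = 0.9 it is 0.20 × √0.2 = 8.9%. So the answer depends on the scale.

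**5. Adding selection and the threshold route.** Suppose children enrol only above a cutoff and that cutoff also serves as the clinical threshold (an assumption, since neither value is given). At c = 0.25, r = 0.8, the share of unchanged children meeting the full rule is 34% with the cutoff at the mean and 45% with it one SD above; without selection, the 10% rule alone gives 26%.

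**6. Size of a reliable change.** This is 1.96 × √2 × SEM, with SEM = SD√(1 − r). At c = 0.30, r = 0.8: SEM = 0.30 × √0.2 = 0.134, and 1.96 × 1.414 × 0.134 = 0.37, or 37% of the mean score.

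**The case against.** The strongest reply is that the documents give no SD, reliability or score range for either scale, so the size of the problem rests on assumptions. That stands. A reader might infer that 10% simply lies within ordinary retest variation and that many unchanged children will be counted as improved. The documents do not support this as a fact: with an SD of 20% and reliability 0.9, the SD of retest change is 8.9%, already below the cut, and with a reliable scale of small relative spread the false-positive share is 2% to 6%. Normed scores could fall in that region.

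The reach of the one-point example is also unknown. No section says which scores are 10 or less, and children enter with at least one raised subscale.

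The consequence is limited too. The rule concerns secondary outcomes; the primary outcome does not use it. If the paired t-tests compare scores, the cut affects only a reported responder share, although the word outcomes in that sentence leaves some doubt about what is tested. A looser secondary rule is a defensible choice in an open-label pilot, and the lack of a control arm limits any responder share, whatever the cut.

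None of this supplies a basis for 10% or a minimum fall for the threshold route.

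**Conclusion.** The point holds in conditional form and is worth acting on because correction is cheap. The 10% cut is unjustified in the plan. Over SDs of 20% to 40% of the mean and reliabilities of 0.7 to 0.9, roughly one unchanged child in eight to somewhat more than one in three would meet it on a given score, before the threshold route and selection on high scores are counted. Those features can raise the share further. In a single-arm trial of 20, the reported share of anxiety positive outcomes could therefore be largely measurement noise.

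Three stronger inferences should be resisted. The evidence on the primary outcome is not weakened by this rule. The rule is not shown to produce anxiety responders whom the CGI-Improvement rating calls non-responders: that rating also covers seizure control, so the two can disagree under any cut. Nor does it follow that a stricter fixed percentage, such as 30%, would settle the matter. That figure has no basis in the documents and is below the 37% reliable change at SD 30% and reliability 0.8.

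**What to change.** Amend the secondary-outcome paragraph of the Statistical Analysis Plan as follows.

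- For the PARS and MASC totals, define a positive outcome as a fall larger than that scale's reliable change, 1.96 × √2 × the standard error of measurement, computed from a cited retest reliability and SD.
- Name one score version, raw or normed, for each scale.
- State the value of the clinical threshold, and count a drop below it only when the fall also exceeds the reliable change.
- Report subscales as mean change, with no percentage rule.
- Show each child's percent change so that readers can apply other cut-offs.
- Say that the paired t-tests are run on the scores.

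This needs a literature value for each scale and a wording change, but no new data. The downside is a lower reported share of positive secondary outcomes. The change does not replace a control: children selected on high scores can still fall by regression to the mean, so the share should remain descriptive. The 10% rule as placed also covers the Quality of Life in Epilepsy Scale, which this wording does not address and which needs its own stated criterion.
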